**6.2 Study Time points**

Unless otherwise specified, these study time point definitions are for Study 20140159 only.

**Enrollment date**

The date the subject has met all eligibility criteria and eligibility has been completed in the IVR/IWR system.

**Study Day 1**

The date that the initial dose of IP is administered in Study 20140159. For subjects who didn't take any IP throughout the study, leave as missing.

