# 4. SUBJECT ELIGIBILITY

Before any study-specific activities/procedure, written informed consent must be obtained (see Section 11.1). In addition to written informed consent from a legally acceptable representative, the assent of the child also must be obtained, as appropriate and if requested by the institutional review board/independent ethics committee (IRB/IEC).

Subjects from the cinacalcet arm of Study 20130356 or subjects in Study 20110100 who had their dose withheld at the EOIP visit, may enroll in this study if they meet eligibility criteria but will not restart dosing until the criteria for restarting dosing, defined in Section 6.2.3, are met.

Subjects who were  $\leq$  18 years old at week 20 in the 20130356 study or at the time of study termination, are eligible to enter this Study 20140159 even if they have already turned 18 years of age or are due to turn 18 years of age during their planned participation in the 20140159 study.

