#### CONFIDENTIAL

# Page 30 of 79

For subjects with  $\leq$  14 days between the last dose of cinacalcet in Study 20110100 and Study 20140159 day 1, subjects will continue the same dose of cinacalcet they received at the completion EOIP visit or early termination visit at Study 20110100 termination and follow the weekly dose adjustments outlined in Table 2. Dose titration cannot occur until week 4. If subjects from the Study 20110100 are on a dose withhold at day 1 of Study 20140159, the iPTH and cCa restart values (iPTH > 150 pg/mL and cCa > 9.0 mg/dL) must be reached prior to resuming cinacalcet in the Study 20140159.

Dose adjustments for subjects receiving cinacalcet will be assessed at each weekly visit during the treatment period. The daily dose of cinacalcet may only be increased at monthly titration visits (week 4, 8, 12, 16, 20, and 24); it can't be increased at any other time during the treatment period. At all weekly visits (including week 4, 8, 12, 16, 20, and 24), the dose may be maintained, reduced or withheld based upon the criteria in Table 2.

If any of the criteria for dose withholding are met at any time during the trial, including between scheduled study visits (ie, unscheduled), the dose of cinacalcet is to be withheld until all of the following criteria are met:

- central laboratory corrected calcium value is >9.0 mg/dL
- iPTH is >150 pg/mL
- ionized calcium is >1.13 mmol/L
- subject has no symptoms of hypocalcemia
- subject doesn't have any ongoing adverse event(s) which warrant withholding of cinacalcet.

If a subject dose is being withheld, ionized calcium levels should be assessed weekly until an ionized calcium of >1.13 mmol/L is obtained, at which point, cCa and iPTH should be assessed by the central laboratory.

Once all the restart criteria above are met, cinacalcet may be restarted at one PSD below the previous dose received. Subjects receiving the lowest PSD (1 mg) who require a dose reduction will have their dose withheld until the criteria for maintaining or increasing the dose are met, at which time they will restart dosing at 1 mg/day.

If subjects require temporary administration of concomitant medications that are known to prolong the QTc interval, are CYP3A4 inhibitors, or are CYP2D6 substrates, the administration of IP is to be withheld. The dose may be restarted at one PSD below the previous dose once the treatment with the concomitant medication has completed and all of the restart criteria above are met.

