#### 7.2 General Study Procedures

All on-study visits and dosing should be scheduled from day 1. Week 1 begins one week after the day 1 visit. It is important to perform study assessments and obtain samples at the time points outlined in the Schedule of Assessments in Section 7.1.

The duplicate study assessments will be collected once for both studies as described in Section 7.2.2.

When it is not possible to perform a study visit at the specified time point, the visit may be performed within  $\pm$  3 days. If a study visit is missed, subsequent visits should resume on the original visit schedule. Missed assessments at prior visits should not be duplicated at subsequent visits.

With the exception of screening assessments, all study procedures for a visit must be completed on the same day.

It is the responsibility of the investigator to ensure that all procedures are performed according to the protocol.

Any blood or serum collected according to the Schedule of Assessments may be analyzed for any of the tests outlined in the protocol and for any tests necessary to ensure subject safety. This includes testing to ensure analytical methods produce reliable and valid data throughout the course of the study. This may also include, but is not limited to, investigation of unexpected results, incurred sample reanalysis, and analyses for method transfer and comparability.

Details regarding each type of procedure are provided in Section 7.3

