**Study day**

For a given study visit, the study day is defined as: study day = (visit date - date of Study Day 1) +1.

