**Analysis window for vital signs and all other labs.**

Study Visit	Target Day	Study Day	Interval (days)
Baseline	1	≤ 1	N/A
Week 3	22	2-36	35
Week 7	50	37-64	28
Week 11	78	65-92	28
Week 15	106	93-120	28
Week 19	134	121-148	28
Week 23	162	149-176	28
Week 27	190	177 – 194	18
Week 28	197	195 – 211	17
Week 32	225	≥212	N/A

If there is more than one observation in a visit window, use the value collected closest to the target day. If multiple observations are equally close to the target day, use the later value.

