#### StudyBaseline Values

##### StudyBaselineatStudyDay1ofStudy20140159

Study Baseline iPTH, corrected total serum calcium, and serum phosphorus values are defined as the mean values of samples collected during the screening period and Study Day 1 pre-dose.

---

Product: Cinacalcet HCl  
Statistical Analysis Plan: 20140159  
Date: 24 May 2016

Page 13 of 36

---

Ca x P will be calculated at central lab COVANCE using corrected total serum calcium and serum phosphorus. **Study** Baseline value will be the mean of the values during the screening period and **Study** Day 1 pre-dose.

Study Baseline dry weight is defined as the value collected at **Study 20140159** Day 1 visit.

For all other variables, the **study** baseline value is defined as the last non-missing value collected prior to the first dose of IP, either during the screening phase or on Study Day 1.

All **study** baseline values will be calculated to the same number of decimal places as the raw data.

**Study**Baseline vitamin D use

Vitamin D use at **study** baseline is defined as any use of nutritional vitamin D or vitamin D sterol within 7 days prior to Study Day 1.

**Study**Baseline growth hormone use

Growth hormone use at **study** baseline is defined as any use of growth hormone during the screening period prior to Study Day 1.

**Study**Baseline phosphate binder use

Phosphate binder use at **study** baseline is defined as any use of any phosphate binder the day prior to Study Day 1.

**Study**Baseline calcium supplement use

Calcium supplement use at **study** baseline is defined as any use of any calcium supplement the day prior to Study Day 1.

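### For children first dosed 14 to 48 days after the day 1 visit, the SAP's first-dose clock puts the off-drug end-of-study calcium, phosphorus and iPTH samples in the Week 28 window of the by-visit safety summaries

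*SAP*

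**What the plan says.** **Visit schedule.** Protocol 7.2 states: "All on-study visits and dosing should be scheduled from day 1. Week 1 begins one week after the day 1 visit". Protocol 3.1 counts the 28 treatment weeks from enrolment, so neither the Week 28 end-of-investigational-product (EOIP) visit nor the Week 32 EOS visit moves with a late first dose.

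**Late starters are foreseen.** Under Protocol 4, former cinacalcet-arm or 20110100 children whose dose was withheld at the parent EOIP visit "may enroll in this study if they meet eligibility criteria but will not restart dosing until the criteria for restarting dosing" are met. Protocol 6.2.3.1.2.1 makes the same provision for children under 2 who "are on a dose withhold at day 1 of Study 20140159". Sections 6.2.3.1.1 and 6.2.3.1.2.2 do so for the other groups.

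**Analysis clock.** SAP 6.2 sets Study Day 1 as "The date that the initial dose of IP is administered in Study 20140159" and defines "study day = (visit date - date of Study Day 1) +1". Actual visit dates are mapped to analysis visits on that clock. Within a window: "If there is more than one observation in a visit window, use the value collected closest to the target day", and a tie goes to the later value.

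**Off-drug data.** SAP 10.1 excludes labs drawn more than 7 days after last dose, for the efficacy analyses only. SAP 10.7.2 and 10.7.3 state no such exclusion.

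**Baseline.** Under SAP 6.3, study baseline iPTH, corrected calcium (cCa) and phosphorus "are defined as the mean values of samples collected during the screening period and Study Day 1 pre-dose". Other variables, apart from Ca x P and dry weight, use the last non-missing value before first dose.

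**The concern.** Visits follow one anchor and the analysis windows another, and no rule connects them. For a child first dosed on the day 1 visit the anchors coincide. For a child who starts later, each scheduled visit moves earlier on the SAP clock by the length of the delay. A sample drawn about four weeks after treatment stopped can then be reported as an on-treatment Week 28 value, while the true end-of-treatment sample takes another label or is not selected.

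Hypocalcemia is a central risk here, and late starters may include children withheld for low calcium. In groups this small, a few off-drug calcium values can move a Week 28 by-visit summary.

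**Working it through.** **Inputs.** Let d be the days from the day 1 visit to first extension dose. The documents give no values of d, so a range is used.
- Scheduled visit at week w: day 7w + 1 from the day 1 visit (Protocol 7.2).
- SAP study day of that visit: 7w + 1 − d (SAP 6.2).
- iPTH and Ca/cCa/P windows: Week 19, 121–148; Week 23, 149–176; Week 28, 177–211 (target 197); Week 32, 212 or later.
- Vital signs and all other labs: Week 27, 177–194; Week 28, 195–211.

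**The plan's own figures at d = 0.** Week 28: 7 × 28 + 1 = 197. Week 32: 7 × 32 + 1 = 225. Width: 211 − 177 + 1 = 35 days. All match the SAP.

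**iPTH, Ca, cCa and P** (study day, with the window it falls in)

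| d | Week 23 visit | EOIP | EOS | Week 28 value, no off-drug cut | Week 28 value, 7-day cut applied first |
|---|---|---|---|---|---|
| 0 | 162 (W23) | 197 (W28) | 225 (W32) | EOIP | EOIP |
| 13 | 149 (W23) | 184 (W28) | 212 (W32) | EOIP | EOIP |
| 14 | 148 (W19) | 183 (W28) | 211 (W28) | EOS | EOIP |
| 20 | 142 (W19) | 177 (W28) | 205 (W28) | EOS | EOIP |
| 21 | 141 (W19) | 176 (W23) | 204 (W28) | EOS | none |
| 28 | 134 (W19) | 169 (W23) | 197 (W28) | EOS | none |
| 48 | 114 (W15) | 149 (W23) | 177 (W28) | EOS | none |
| 49 | 113 (W15) | 148 (W19) | 176 (W23) | none | none |

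EOS lies in the Week 28 window when 177 ≤ 225 − d ≤ 211, that is d = 14 to 48. With EOS 3 days early the range is 11 to 45; 3 days late, 17 to 51. At d = 14 EOIP and EOS are each 14 days from target (197 − 183 and 211 − 197), so the later one, EOS, is used. Above 14 EOS is closer, and from d = 21 EOIP has left the window.

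**Vital signs and other labs.** EOS is labelled Week 28 when 195 ≤ 225 − d ≤ 211 (d = 14 to 30), and Week 27 when 177 ≤ 225 − d ≤ 194 (d = 31 to 48).

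**How far off drug.** EOS follows EOIP by 225 − 197 = 28 days, or 22 to 34 with ±3-day visits. The 7-day rule therefore removes EOS wherever it applies.

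**Efficacy.** The SAP does not say whether the cut comes before or after window selection.
- Before: at d = 14–20 the Week 23 window is empty; at d = 21–48 EOIP is labelled Week 23 and Week 28 is empty.
- After: at d = 14–20 EOS is selected and then dropped, so the on-drug EOIP value can be lost as well.
- Week 11 also shifts: at d = 14 the week 15 visit is day 106 − 14 = 92, inside the Week 11 window (65–92).

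The exposed 20140159-only endpoints are change in cCa and phosphorus, mean iPTH ≤ 300 pg/mL, and cCa and phosphorus at weeks 11 and 28. The iPTH-reduction endpoints use only the former SOC arm, who cannot enter on a cinacalcet withhold.

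**Baseline, rules side by side.** SAP 6.1 ends screening at enrolment. Protocol 6.2.3.1 calls for central cCa and iPTH once ionized calcium recovers, which for a late starter is after enrolment. That restart sample enters the SAP 6.3 mean only if drawn on Study Day 1. The SAP 6.2 tables, however, label any sample at study day ≤ 1 as Baseline. At d = 28 the Week 3 sample is day 22 − 28 = −6: Baseline by the tables, but neither a screening nor a Study Day 1 sample under 6.3.

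**The case against.** **First-dose anchoring is a legitimate convention.** The protocol glossary uses it, and Amendment 1 adopted it deliberately. Moving every window to the day 1 visit would create a similar error: at d = 28 the Week 1 and Week 3 samples (days −20 and −6) precede any extension dose yet would be labelled on-treatment. This stands, and the fix must allow for it.

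**The safety sections speak of scheduled or protocol-specified time points**, which could be read as nominal visits. But SAP 6.2 maps actual dates to study visits through the windows, and nothing in 10.7 overrides that.

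**SAP 10.6.2 already examines dose interruption.** It covers gaps over 14 days between parent EOIP and Study Day 1, but only for combined-study iPTH endpoints, and does not change the windows.

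**Readings that a reader might infer, but that go too far:**
- *Every child enrolled on a withhold is mislabelled.* At d = 0 to 13 EOS stays in Week 32.
- *The main safety result is biased toward better calcium.* Event-of-interest incidence does not use visit windows. The calcium-threshold incidences count values during the study, and shifts take the worst grade at any visit. Ionized calcium is not scheduled at EOS. Withholds may also follow low iPTH, adverse events or excluded medication, so the direction of any shift is not general.
- *Baseline is the value that triggered the withhold.* A withhold already running at day 1 was triggered earlier; screening and day 1 samples are taken during it, whichever anchor is used. Combined-study baselines for prior-cinacalcet children come from the parent study and are unaffected.

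**Conclusion.** The point holds for first-dose delays of 14 to 48 days, assuming visits on their nominal days. Its main effect is on the by-visit descriptive safety summaries of labs and vital signs. Efficacy is protected from the EOS value but can have shifted or empty Week 23 and Week 28 windows. The post-baseline relabelling leaves the primary endpoint, threshold incidences and worst-grade shifts unchanged.

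The number affected cannot be computed. Those who could in principle enter on a withhold are at most about 24 (half of 48) + 30 = 54 of 78. An assumed 5–20% of 54 gives about 3 to 11, but only those with a 14–48 day delay would be mislabelled, and the documents give no share for either group.

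The baseline problem is separate from the anchor: the SAP has two rules that can give different values. As an illustration only, a child at cCa 8.0 mg/dL in screening who restarts just above 8.4 has a baseline more than 0.4 below the restart value if no Study Day 1 sample exists. With a Study Day 1 value of 8.4 the mean is (8.0 + 8.4)/2 = 8.2, and the gap is 0.2.

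**What to change.** In SAP 6.2, 6.3 and 10.1:

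1. For subjects first dosed after the day 1 visit, map labs and vital signs by nominal visit, and show samples taken before first dose as pre-treatment rather than as on-treatment weeks.
2. For all subjects, remove samples taken more than 7 days after last dose before window selection, for every on-treatment visit through Week 28, in safety as well as efficacy summaries. Report EOS only as Week 32 follow-up.
3. For delayed starters, define study baseline iPTH, cCa and phosphorus as the last value before first dose, matching the rule SAP 6.3 already uses for most other variables.

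The cost is SAP wording and programming with visit and dose dates already collected. The downside is that for late starters the week label no longer equals weeks on drug.

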**Day 1 of cinacalcet treatment (combined studies 20130356, 20110100 and 20140159)**

The date that the initial dose of cinacalcet treatment is administered in studies 20130356, 20110100 or 20140159.

**Study day**

For a given study visit, the study day is defined as: study day = (visit date - date of Study Day 1) +1.

**Cinacalcet day (combined studies 20130356, 20110100 and 20140159)**

For a given study visit, the cinacalcet day is defined as: cinacalcet day = (visit date – date of Day 1 of cinacalcet treatment) +1.

**End of treatment**

For subject who completed treatment as of cutoff date, the end of treatment is defined as the date of the last dose of IP. If subject is ongoing as of cutoff date, leave as missing.

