#### 6.2.3.1.1.1 Dosage Adjustments

The initial dose of cinacalcet and all subsequent doses will be calculated by the site staff and confirmed by the IVR/IWR system. Subjects from the SOC arm will start at the initial cinacalcet dose of 0.20 mg/kg/day, based on the subject's dry weight at day 1 of Study 20140159, rounded down to the lowest PSD.

Subjects from the cinacalcet arm with  $\leq$  14 days between the last dose of cinacalcet treatment in Study 20130356 and day 1 of Study 20140159 will start cinacalcet dosing at the same dose they received at the completion of the EOIP visit and follow weekly dose adjustment based on the Table 1. For subjects from the cinacalcet arm with > 14 days between the last dose of cinacalcet treatment in Study 20130356 and day 1 of

AMGEN

Page 26 of 79

Page 27 of 79

Study 20140159, the initial dose of cinacalcet will be 0.20 mg/kg/day, based on the subject's dry weight at day 1 of 20140159, rounded down to the lowest PSD, will be assigned.

Dose adjustments for subjects receiving cinacalcet will be assessed at each weekly visit during the treatment period. The daily dose of cinacalcet may only be increased at monthly titration visits (week 4, 8, 12, 16, 20, and 24); it can't be increased at any other time during the treatment period. At all weekly visits (including week 4, 8, 12, 16, 20, and 24), the dose may be maintained, reduced or withheld based upon the dose adjustment criteria in Table 1.

If any of the criteria for dose withholding are met at any time during the trial, including between scheduled study visits (ie, unscheduled), the dose of cinacalcet is to be withheld until all of the following criteria are met:

- central laboratory corrected calcium value is >8.4 mg/dL
- iPTH is > 150 pg/mL
- ionized calcium is >1.05mmol/L
- subject has no symptoms of hypocalcemia
- subject doesn't have any ongoing adverse event(s) which warrant withholding of cinacalcet.

If a subject dose is being withheld, ionized calcium levels should be assessed weekly until an ionized calcium of >1.05 mmol/L is obtained, at which point, cCa and iPTH should be assessed by the central laboratory.

Once all the restart criteria above are met, cinacalcet may be restarted at one PSD below the previous dose received. Subjects receiving the lowest PSD (2.5 mg) who require a dose reduction will have their dose withheld until the criteria for maintaining or increasing the dose are met, at which time they will restart dosing at 2.5 mg/day.

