**End of dose titration phase**

The end of dose titration phase is Week 24 of Study 20140159.

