**The laboratory data collected more than 7 days after the last dose of IP will be excluded for the efficacy analyses.**

**For the interim analysis supporting pediatric sNDA, only data from the 20140159 study before interim data cutoff date will be analyzed according to the actual treatment received from the parent study and overall.**

**For the final analysis, final efficacy and safety data from Study 20140159 will be analyzed. In addition, cumulative data combining the parent studies (20130356 and 20110100) and Study 20140159 will also be summarized.**

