#### Study20140159only

Proportion of subjects achieving the secondary endpoints of  $\geq 30\%$  reduction in iPTH from study baseline to mean value during weeks 11 and 15 will be reported with 95% CI based on 20130356 SOC Set. Subjects who have no iPTH values during weeks 11 or 15 will be considered non-responders.

Proportion of subjects achieving the secondary endpoints of  $\geq 30\%$  reduction in iPTH from study baseline to mean value during weeks 23 and 28 will be reported with 95% CI based on 20130356 SOC Set. For subjects who do not have a iPTH value during weeks 23 and 28, the mean of the last two available post-baseline values in the dose-titration phase will be used. If only one post-baseline value is available, this single value will be used. If no post-baseline value is available, the subject is considered a non-responder.

Summary statistics will be provided for percent change from study baseline to mean iPTH during weeks 23 and 28 based on 20130356 SOC Set, and change in corrected total calcium and change in serum phosphorus from study baseline to mean value during weeks 23 and 28 based on efficacy analysis set by treatment group in the parent studies. For subjects who are missing the efficacy measurement during weeks 23 to 28, the mean of the last two available post-baseline values in the dose titration phase will be used. If only one post-baseline value is available, this single value will be used. If no post-baseline value is available, the subject will be excluded from the analysis.

Proportion of subjects who achieve a mean iPTH value  $\leq 300$  pg/mL during weeks 23 and 28 will be provided based on efficacy analysis set by the treatment group in parent study with 95% CI. For subjects who do not have an iPTH value during weeks 23 and 28, the mean of the last two available post-baseline values in the dose-titration phase will be used. If only one post-baseline value is available, this single value will be used. If no post-baseline value is available, the subject is considered a non-responder.

**Summary statistics will be provided for serum cCa and phosphorus values at study baseline, week 11, and week 28 for all efficacy analysis set subjects.**

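### The 7-day cut after the last dose treats unresolved and resolved dose holds differently at weeks 23 and 28

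*SAP*

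**What the plan says.** The operative rule is in SAP 10.1: "The laboratory data collected more than 7 days after the last dose of IP will be excluded for the efficacy analyses". It does not mention dose holds and does not say which last dose is meant.

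Two other places suggest one final date per child. The end-of-treatment entry in SAP 6.2 reads: "For subject who completed treatment as of cutoff date, the end of treatment is defined as the date of the last dose of IP". SAP 10.6.3 runs its laboratory summaries to 7 days past the last dose. SAP 6.2 adds, for a data cutoff: "If subject is ongoing as of cutoff date, leave as missing".

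For the week 23/28 endpoints, SAP 10.6.1 fills gaps: "For subjects who do not have a iPTH value during weeks 23 and 28, the mean of the last two available post-baseline values" from the titration phase are used. The calcium and phosphorus changes have a parallel rule. SAP 6.1 sets the end of that phase: "The end of dose titration phase is Week 24 of Study 20140159".

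Protocol 6.2.3.1.1.1 makes holds open-ended: "the dose of cinacalcet is to be withheld until all of the following criteria are met". The restart criteria for children from Study 20130356 are corrected calcium above 8.4 mg/dL, iPTH above 150 pg/mL, ionized calcium above 1.05 mmol/L, no symptoms of hypocalcemia and no adverse event that warrants withholding. The child is followed meanwhile: "If a subject dose is being withheld, ionized calcium levels should be assessed weekly until an ionized calcium of >1.05 mmol/L is obtained". Protocol Table 4 schedules iPTH, calcium and phosphorus at weeks 23 and 28 without reference to dosing. Protocol 12.4 asks for data collection also from subjects who are not receiving protocol-required therapy. A long hold is not itself a listed reason for removal in Protocol 8.2.

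**The concern.** Take two children who stop cinacalcet on the same day because a hold criterion is met. Both stay on study and give blood at week 23.

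One recovers and restarts. The last dose now lies after week 23, so the off-drug week 23 value is kept. The other does not recover. The last dose stays before the hold, so the same kind of value is discarded and, if the hold began early enough, replaced by earlier values taken mostly on drug.

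What separates them is whether calcium, iPTH and symptoms recovered enough to restart. Calcium and iPTH are themselves endpoint variables, so selection into the analysis is related to the outcome. The discarded values are scheduled and observed, from a child still in follow-up. This is not ordinary dropout. The Study 20140159 endpoints concerned also enter the interim analysis that supports the pediatric filing (SAP 4 and 8).

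**Working it through.** **Inputs**
- iPTH, calcium and phosphorus windows (SAP 6.2): week 23 is days 149-176, target 162; week 28 is days 177-211, target 197.
- Visit tolerance: ±3 days (Protocol 7.2).
- Planned size: about 48 plus 30 (SAP 3.2). Allocation in Study 20130356 is 1:1 (Protocol 2.5.1).
- Entry iPTH for former standard-of-care children: at least 300 pg/mL (Protocol 4.1.1).

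**The plan's own figures.** 48 + 30 = 78, as printed. 7 × 23 + 1 = 162 and 7 × 28 + 1 = 197, as printed. Window lengths are 176 - 149 + 1 = 28 and 211 - 177 + 1 = 35, as printed.

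**Which final-dose days remove which values.** A value is removed if its day exceeds the final dose day plus 7.
- Week 23 is removed if the final dose is on or before 162 - 8 = day 154 (151 to 157 with the visit tolerance).
- Week 28 is removed if it is on or before 197 - 8 = day 189 (186 to 192 with the tolerance).

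For a child with an unresolved hold and samples on target days:
- *Final dose by day 154:* both values go. Substitution applies, using for example weeks 15 and 19 for a final dose on day 140. These values may be up to 7 days off drug, so they are mostly but not always pre-hold.
- *Final dose on days 155-189:* only week 28 goes. Week 23 stands alone and nothing is imputed.
- *Final dose on day 190 or later:* nothing is removed.
- *Hold so early that no post-baseline value survives (for example, final dose on day 10):* non-responder, or excluded from continuous summaries.

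**Illustration (all iPTH values assumed).** Baseline 800, on drug 450, off drug 850 pg/mL. The hold starts after day 140 and is kept open by low calcium while iPTH rises.
- *Hold unresolved, SAP as written:* (450 + 450)/2 = 450; 450/800 - 1 = -43.8%, responder.
- *Same child, observed values:* (850 + 850)/2 = 850; 850/800 - 1 = +6.3%, non-responder.
- *Same hold, restart between days 163 and 190:* week 23 is off drug and kept, and week 28 follows resumed dosing. (850 + 450)/2 = 650; 650/800 - 1 = -18.8%, non-responder.

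**Holds kept open by iPTH itself.** Such a child has iPTH of 150 pg/mL or less. Against the entry minimum, 150/300 - 1 = -50%, beyond the 30% reduction, and 150 is below 300. The child already counts as a success on both iPTH endpoints from observed values, so substitution cannot add a success.

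**Size per child.** The former standard-of-care group is at most about 48/2 = 24. One child reclassified moves that proportion by 1/24 = 4.2 points; at an assumed 20 or 15 children, by 5.0 or 6.7. An overall proportion at 78 moves by 1/78 = 1.3 points.

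**The case against.** Restricting efficacy to values close to dosing is a legitimate on-treatment choice. The endpoints are descriptive and secondary, and the primary endpoint is safety. That limits the weight of the point, but an on-treatment rule should still treat off-drug values in the same way whether or not dosing later resumes.

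The planned sensitivity analyses (SAP 10.6.2) partly probe the substitution. The completer analysis drops children with no week 23-28 value, so a gap from the main result would be informative. The weighting model includes symptomatic hypocalcemia. However, none of the listed analyses says that it restores the excluded values.

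If last dose in SAP 10.1 meant the most recent dose before each sample, the asymmetry would vanish. SAP 6.2 and 10.6.3 point the other way, but SAP 10.1 does not settle it.

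A reader might infer more than the documents support:
- *The end-of-treatment definition removes the values.* It does not. SAP 10.1 stands alone and does not use that variable, which is left missing for a child ongoing at the cutoff.
- *Any late hold triggers replacement.* Only a final dose by about day 154 does.
- *A restarter keeps off-drug values at both visits.* Week 28 normally follows resumed dosing.
- *Children held for low iPTH inflate the response.* They do not, as shown above. Substitution also takes the latest values, not the best.
- *Loss of control is hidden.* The safety laboratory summaries in SAP 10.7.2 report iPTH, calcium and phosphorus at scheduled visits with no 7-day cut.

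**Conclusion.** The unequal handling is real and specific to the week 23/28 efficacy endpoints. At weeks 11/15 the main analysis counts a child with no value as a non-responder.

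The two iPTH proportions can be inflated only when calcium, symptoms, another adverse event or a prohibited medicine keeps the hold open while iPTH rises. The calcium and phosphorus changes are affected whatever keeps the hold open, in a direction the documents do not determine.

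The conclusion assumes that last dose means the final dose and that held children attend weeks 23 and 28 as scheduled. The number of unresolved holds is not given, so the total bias cannot be stated. For scale, with an assumed 12 of 24 responders and an exact interval, losing one changes 50.0% (29.1% to 70.9%) to 45.8% (25.6% to 67.2%). That is small beside the interval, but it is systematic and avoidable. This is a cheap improvement and does not threaten the primary endpoint.

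**What to change.** In SAP 10.1, define the anchor of the 7-day cut as the date of permanent discontinuation of cinacalcet, or the week 28 end-of-investigational-product visit if there was none, rather than the last dose before an unresolved hold. Observed week 23/28 values during open and resolved holds are then used alike. Say also how a child on a hold at the interim cutoff is handled.

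At the least, keep the present rule and add the re-anchored version as a sensitivity analysis in SAP 10.6.2 for the week 23/28 endpoints, reporting how many children have values removed by the cut while on an open hold.

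The cost is SAP wording and one derived date. The inputs are already collected: reasons for dose changes and withholding (SAP 9.3.1) and the time and reason of withdrawal from treatment (SAP 10.2). Dosing and visits do not change. The downside is that some off-drug values enter the efficacy analyses and response rates may be slightly lower.
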